- 2. The EXIT Visit in the respective feeder continuation studies will serve as the Day 0 visit for all 3 subject groups in this study. Assessments covered for both this study at Day 0 and the Exit visit of the feeder continuation studies need only be performed once and recorded in the appropriate case report forms for each study. Subjects in the control group must be able to receive the 1st dose of belimumab on Day 0 of this study on average 4 weeks (minimum of 2 weeks, maximum of 8 weeks) after the last dose in the feeder continuation study.
- 3. The 16 week follow-up visit will occur at approximately 16 weeks after last dose of investigational product for subjects in the control group who withdraw at any time during the study, or for subjects in the treatment holiday group who withdraw from the study from Week 24 onwards (Visit 7) during the belimumab re-introduction period. The 16-week and 6 month follow-up visits do not apply to subjects in the long-term discontinuation group.
- 4. Obtain written informed consent to participate in this study at the Screening visit.
- 5. Guidelines for scoring proteinuria for SELENA SLEDAI are provided in Section 6.3.1.1.
- 6. Complete assessment prior to belimumab dosing for subjects in the control group (to Week 48) and for subjects in the treatment holiday group (during Weeks 24 to 48 or earlier in the event of a flare). Immunogenicity testing includes quantifying the amount of belimumab present in the samples using the belimumab PK assay.
- 7. For any subject whose weight changes by more than 5% from that recorded at Day 0, use the weight at the current visit for calculating the belimumab dose to be administered. Height measured only at Day 0.

2012N154810 06

CONFIDENTIAL

- 8. A 24-hour urine may be done as an additional assessment if clinically indicated (e.g., renal flare).
- 9. Urine pregnancy test results for women of child-bearing potential must be available prior to dosing (during Weeks 0 to 48 in the control group and during Weeks 24 to 48 or earlier in the event of a flare in the treatment holiday group). Can be performed at any time during the visit for females of child-bearing potential in the long-term discontinuation group.
- 10. PGx sampling from consenting subjects recruited from all studies except from study BEL114333. PGx informed consent must be obtained prior to sampling.
- 11. Serum immunoglobulin isotypes: IgG, IgM, IgA.

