6.1.2. Secondary Endpoints

The secondary endpoints are:

- Rate of any SLE Flare Index flares.
- Time to first severe SLE Flare Index flare.
- Number of subjects in the treatment holiday and long-term discontinuation group with evidence of rebound (defined as a SELENA SLEDAI score during the first 24 weeks that exceeds the baseline SELENA SLEDAI score in the original parent study.
- Number of subjects with confirmed true positive belimumab anti-drug antibodies (ADA) by the end of the study.
- Percentage change from baseline in:
 - Total serum immunoglobulin (IgG, and other isotypes: IgM and IgA)
 - Autoantibodies (anti-dsDNA, ANA), and complement (C3, C4)
- Percent change in absolute B cell subsets (CD20+, CD20+/27+ memory, CD20+/27naïve, CD20+/69+ activated, CD20+/138+ plasmacytoid, CD19+/27BRIGHT/38BRIGHT SLE subset and CD20-/138+ plasma cells) at Weeks 0, 8, 16, 24, 32, 40 and 52 and from Weeks 24 to 52.
- Absolute change in SELENA SLEDAI score.
- Number of days of daily prednisone dose ≥7.5 mg/day and/or increased by 25% from Day 0 of this study to Week 24, from Day 0 of this study to Week 52, and from Week 24 to Week 52.
- Number of days of daily prednisone dose ≤7.5 mg/day and/or decreased by 25% from Day 0 of this study to Week 24, from Day 0 of this study to Week 52, and from Week 24 to Week 52.

Note: baseline is the time before any treatment with belimumab, which was Day 0 of the original parent studies that fed into the 3 continuation studies from which subjects were recruited into this study. When Day 0 is used in relation to endpoints, this refers to Day 0 of this study.

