6.4.16. Immunogenicity

Serum samples will be collected for immunogenicity assessment. All samples should be collected prior to dosing (where appropriate) as specified in the appropriate Time and Events schedule (Table 2 or Table 3). Note that serum samples for immunogenicity must be collected pre-dose at the time of dosing from subjects in the treatment holiday group who experience a severe flare prior to Week 24 and consequently receive open-label

CONFIDENTIAL

belimumab as rescue. For non-dosing visits, assessment can be performed at any time during the visit. An attempt will be made to determine the amount of belimumab (PK) present in immunogenicity samples with confirmed anti-drug binding antibodies (ADA). The belimumab level in these samples will be used in the interpretation of ADA results and will be included in the immunogenicity section in the CSR.

An attempt will be made to obtain a serum sample for anti-belimumab antibodies at least 6 months after the last dose of belimumab for any subject who had an anti-belimumab antibody response at the 16-week follow-up visit or if the 16-week follow-up immunogenicity sample is not available.

All immunogenicity testing will be carried out according to the multi-tier assay testing scheme including the detection of anti-drug binding antibodies (ADA, including 3-steps of screening, confirmation/specificity and titration) and the detection of anti-drug neutralizing antibodies (Nab). **Note:** Nab testing will not be performed in China.

All samples will be tested in ADA screening step. Any samples tested positive in the screening step will then be tested using an ADA confirmation step. Any confirmed positive samples in the confirmation will be further tested in the titration to obtain ADA titer values and in the Nab assay to evaluate the presence of neutralizing antibodies. The incidence of subjects with confirmed positive ADA responses with titers and positive Nab will be reported, respectively at the end of the study. However, Nab results will not be available for China subjects.

Details for sample processing and analysis are provided in the SPM.

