6.6. Pharmacokinetics

Collect blood samples for measurement of serum belimumab concentrations from subjects in the treatment holiday and control groups at selected sites at the times specified in the Time and Events Table (Table 2). Only one PK sampling for the treatment holiday group between Weeks 0 and 16 can be performed at any time during the visit. Otherwise, sampling must be performed prior to dosing (pre-dose sample) at Day 0 and Weeks 8 and 16. Sampling must be performed pre-dose and post-dose (at the end of the belimumab infusion) at Weeks 24 and 52 (or earlier if belimumab is re-started before Week 24 in the event of a severe flare by using the escape option). For non-dosing visits, assessment can be performed once at any time during the subject's visit. Subjects in the long-term discontinuation group will have one PK sampling performed at any time during the visit between Weeks 0 and 24. PK sampling for the long-term discontinuation group is not performed after Week 24. Long-term discontinuation subjects withdrawing before Week 24 will have one PK sampling performed at any time during the EXIT visit. PK sampling for long-term discontinuation subjects withdrawing after Week 24 is not performed at the EXIT visit. Samples will be analysed at a central laboratory. PK assessment will also be used to determine belimumab concentration in confirmed positive immunogenicity samples.

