2.2. Study Objective(s) and Endpoint(s)

Objectives	Endpoints
Primary Objectives	Primary Endpoints
 Characterize the efficacy of a 24-week withdrawal followed a 28-week reintroduction of intravenous belimumab thera compared with uninterrupted intravenous belimumab thera for 52 weeks in subjects with SLE disease activity receivin belimumab 10 mg/kg plus standard of care, as measure by time to first flare. 	by ipy low g
Secondary Objectives	Secondary Endpoints
• Evaluate the rate of any flare	 Rate of any SLE Flare Index flare per subject year. Time to first SLE Flare Index severe flare.
 Assess safety. 	 Adverse events AESI Laboratory parameters Vital signs
Assess SLE disease activity.	 Number of subjects in the treatment holiday and long-term discontinuation group with evidence of rebound (defined as a SELENA SLEDAI score during the first 24 weeks that exceeds the baseline SELENA SLEDAI score in the subjects' respective original parent study). SELENA SLEDAI scores change from baseline.
Assess immunogenicity.	Response (Negative, Transient Positive, Persistent Positive) by Visit and Across All Visits
 Assess markers of autoimmuresponse (e.g., immunoglobulins, compleme 	anti-dsDNA, ANA, C3, and C4.

Objectives	Endpoints	
	(CD19+, CD20+, CD20+/27+ memory, CD20+/27– naïve, CD20+/69+ activated, CD20+/138+ plasmacytoid, CD19+/27BRIGHT/38BRIGHT SLE subset and CD20-/138+ plasma cells) at Weeks 0, 8, 16, 24, 32, 40 and 52 and from Weeks 24 to 52.	
 Assess changes in corticosteroid use. 	 Number of days of daily prednisone dose ≥7.5 mg/day and/or increased by 25% from Day 0 of this study to Week 24, from Day 0 of this study to Week 52, and from Week 24 to Week 52. 	
	 Number of days of daily prednisone dose ≤7.5 mg/day and/or decreased by 25% from Day 0 of this study to Week 24, from Day 0 of this study to Week 52, and from Week 24 to Week 52. 	
Exploratory/Other	Exploratory/Other Endpoints	
	Time to first renal flare	
	 Time to first renal flare among subjects with baseline proteinuria >0.5g/24hr equivalent 	
	Change from Baseline in PGA	
	 Change and percentage change from Baseline in BLyS Protein 	
	SLICC/SDI	
	Change from Baseline	

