5.3. Baseline Definitions

5.3.1. Baseline Definitions¹

The baseline (BL) definition is dependent upon the endpoint being analyzed.

• For the SELENA SLEDAI (including rebound), immunoglobulins, autoantibodies, complement, BLyS and B-cell endpoints, baseline is defined as the Day 0 assessment in the subject's respective parent study, prior to exposure with study treatment (whether placebo or belimumab). Baseline data for these

parameters will be extracted from the ADaM data sets from the double blind study (LBSL02, BEL110751, BEL113750 or BEL112341) from which the patients are enrolled.

- For the SLE flares, SLE severe flares, SLICC, prednisone (7 day average prior to Day 0), PGA, and immunogenicity², endpoints, baseline is the Day 0 assessment in BEL116027.
- For other endpoints, baseline is the Day 0 assessment in BEL116027².

¹Feeder study BEL114333 database had not yet completed at the time of BEL116027 Last Patient Last Visit. Consequently, baseline data for BEL114333 patients has not been fully cleaned when extracted from that study's database for reporting.

²Assessments covered for both Day 0 in BEL116027 and the Exit/Follow-up visit of the feeder continuation studies were only to be performed once and were to be recorded in the appropriate case report forms for each study. For Day 0 values not recorded in BEL116027 CRF but exist in the feeder study, the data will be extracted from the appropriate feeder study for inclusion in analysis

In the displays, the baseline value/visit will be denoted as Baseline.

See Section 13.4.1 for a diagram depicting the baseline definitions and phases.

Definition	Reporting Details
Change from Baseline	= Post-Dose Visit Value – Baseline
% Change from Baseline	= 100 x [(Post-Dose Visit Value – Baseline) / Baseline]
Maximum Change from Baseline	= Calculate the change from baseline at each given timepoint
	and determine the maximum change

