8.4.2. Summary Measure

8.4.2.1. Immunogenicity

Immunogenic response will be summarized by visit and anytime postbaseline for the 52-week treatment phase.

Categories of response are Negative, Transient Positive (defined as a single positive response that does not occur at the final assessment, or Persistent Positive (defined as a positive response that occurs on at least 2 consecutive assessments or a single result at the final assessment).

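### The post-baseline antibody summary does not separate subjects already antibody-positive at Day 0 from those who become positive during the study

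*SAP*

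**What the plan says.** **Endpoint.** Protocol 6.1.2 asks for a cumulative count: "Number of subjects with confirmed true positive belimumab anti-drug antibodies (ADA) by the end of the study". SAP 2.2 restates it as "Response (Negative, Transient Positive, Persistent Positive) by Visit and Across All Visits". SAP 8.4.2.1 then says "Immunogenic response will be summarized by visit and anytime postbaseline for the 52-week treatment phase". A lone positive that is not the last assessment is Transient; the other positive category is "Persistent Positive (defined as a positive response that occurs on at least 2 consecutive assessments or a single result at the final assessment"). Neither definition uses the Day 0 result, a rise in titre or the drug level.

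**Baseline.** For a list of endpoints that includes immunogenicity, SAP 5.3.1 says "endpoints, baseline is the Day 0 assessment in BEL116027". SAP 13.4.1 places a Day 0 antibody sample in the pre-study phase. Protocol 4.2 requires at least 6 months of prior belimumab. Protocol 8.1.4 promises an antibody summary at baseline as well as later. The listed displays are one table (3.51, by visit) and one subject listing (47).

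**Sampling.** Protocol Table 2, footnote 13, schedules post-baseline antibody samples at Weeks 12, 24, 36 and 52 in all groups, plus Week 20 in the holiday group only.

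**Drug level in antibody samples.** Protocol 6.4.16: "An attempt will be made to determine the amount of belimumab (PK) present in immunogenicity samples with confirmed anti-drug binding antibodies (ADA"). Protocol 6.6: "PK assessment will also be used to determine belimumab concentration in confirmed positive immunogenicity samples". Table 2, footnote 6, carries no such limit: "Immunogenicity testing includes quantifying the amount of belimumab present in the samples using the belimumab PK assay".

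**The concern.** The study asks what happens to immunogenicity when belimumab is stopped for 24 weeks and then restarted. The useful quantity is therefore antibody that appears during or after the holiday. The planned categories mix it with antibody carried over from the feeder study. The SAP does condition on baseline elsewhere: immunoglobulins are repeated by whether the subject was below or at/above the lower limit of normal at baseline (SAP 8.3.2.4), and autoantibodies are shown again for subjects positive at baseline (Tables 5.3 and 5.4). Immunogenicity gets no such split.

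There is a secondary issue. The protocol intends to use drug level in reading antibody results, but its text limits that measurement to confirmed positives. A negative taken while drug is circulating is the result whose meaning may depend on it.

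**Working it through.** The documents give no antibody rate, power or assay drug tolerance, so there is no stated figure to reproduce. Group sizes are those in SAP 2.3: 12 holiday, 29 control, 39 long-term discontinuation, and 12 + 29 + 39 = 80 agrees with the stated total.

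**1. What the rule does with three subjects**

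| Day 0 | Later results | Class under SAP 8.4.2.1 | Meaning |
|---|---|---|---|
| Negative | Positive at Weeks 36 and 52 | Persistent Positive | New on study |
| Positive | Positive at Weeks 36 and 52 | Persistent Positive | Present before the holiday |
| Positive | All negative | Negative | Positive only if the all-visits wording in SAP 2.2 includes Day 0 |

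The first two rows cannot be told apart in the planned categories. The third depends on which SAP section is followed.

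**2. Weight of one subject.** 1/12 = 8.3%; 1/29 = 3.4%.

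**3. How likely such subjects are.** Day 0 prevalence p is an assumption. Expected number = np; chance of at least one = 1 − (1 − p)^n.

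| Assumed p | Holiday (n = 12): expected, chance | Control (n = 29): expected, chance |
|---|---|---|
| 1% | 0.12, 11% | 0.29, 25% |
| 5% | 0.60, 46% | 1.45, 77% |
| 10% | 1.20, 72% | 2.90, 95% |

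**4. Direction.** With equal Day 0 prevalence and persistence, the expected contribution to the group difference is zero. One carried-over positive in the holiday group alone adds 8.3 points to holiday minus control. One in control alone subtracts 3.4. Nothing in the documents says which is more likely.

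**5. Precision.** Exact 95% intervals are wide: 1/12 gives 0.2% to 38.5%, and 0/29 gives 0% to 11.9%.

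**6. Unequal opportunity.** Post-baseline samples: holiday 5 (Weeks 12, 20, 24, 36, 52), control 4 (Weeks 12, 24, 36, 52). Adjacent pairs: 5 − 1 = 4 against 4 − 1 = 3. A subject positive only at Week 20 is Transient on the holiday schedule and Negative on the control schedule. Positive only at Weeks 20 and 24 is Persistent on the first and Transient on the second. Conversely, positive at Weeks 12 and 24 but negative at Week 20 loses the consecutive pair that the control schedule would give it. The extra visit can only raise the chance of any positive, but can move the Persistent count either way.

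**7. Drug levels.** Separate PK samples, at select sites, fall at Weeks 0, 8, 16, 24, 32 and 52. They coincide with antibody samples at Weeks 0, 24 and 52 only. Negatives at Weeks 12, 20 and 36 have no scheduled level if 6.4.16 governs. If true prevalence is p in both groups, detection is complete off drug, and a fraction s is detected on drug, the spurious gap is p(1 − s). At an assumed p = 10%, s = 100%, 75%, 50% and 25% gives 0, 2.5, 5.0 and 7.5 points; at p = 5%, 0, 1.25, 2.5 and 3.75. These only illustrate scale: neither p nor s is given.

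**The case against.** The best defence is that little is hidden. SAP 2.4 makes every comparison descriptive. The protocol endpoint is a cumulative count, which the plan delivers. A Day 0 positive alone is not a post-baseline result under SAP 13.4.1. Baseline antibody status is summarised by group, and with 12 and 29 subjects a reader could trace individuals through Listing 47. The table shells are available only on request (SAP Appendix 12), so a split could exist there. All of this is fair and limits the importance of the point. However, a group summary at baseline does not link a subject's Day 0 result to the later one, and no table title or SAP text calls for that link. Descriptive status removes testing, not the need to describe the right quantity.

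Three stronger readings are tempting, and the documents do not support them:

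- **That old antibodies will be reported as a holiday effect.** No text attributes antibody differences to the holiday, and carried-over antibodies can occur in either group.
- **That control negatives are masked by drug.** Drug tolerance is not stated. Dosing-day samples are taken pre-dose. A masking difference between groups could arise only through Week 24, because both groups are scheduled to be on drug at Weeks 36 and 52.
- **That limiting the analysis to Day 0 negatives isolates new antibodies.** Day 0 is the feeder study's exit visit, and controls had their last dose 2 to 8 weeks earlier. If drug masks antibodies, some Day 0 negatives may be masked too, and an old antibody that surfaces during washout would look new.

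The conflict over footnote 6 is also mild. The Amendment 05 rationale in Protocol Appendix 8 ties that footnote to confirmed positives, so it reads as loose wording.

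**Conclusion.** The point holds in a limited form. As written, the post-baseline antibody summary pools subjects positive before the holiday with subjects who become positive on study, and SAP 2.2 and 8.4.2.1 leave the role of Day 0 unclear. One subject is worth 8.3 points in the holiday group and 3.4 in control. Whether any such subject exists depends on a Day 0 prevalence that the documents do not give. The distortion has no known direction. Because the groups are small, the split will improve what the table describes without making the group contrast conclusive.

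The drug-level matter is secondary: a wording inconsistency, plus a caution about on-drug negatives that applies only if the assay's drug tolerance is exceeded.

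**What to change.** In SAP 8.4.2.1 and Table 3.51:

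1. Show Day 0 antibody status by group.
2. Show post-baseline Negative, Transient and Persistent counts separately for Day 0 negatives and Day 0 positives, as a descriptive display beside the overall count. Keep the overall count, since it answers the protocol endpoint.
3. State whether the all-visits summary in SAP 2.2 includes Day 0.
4. Add a row restricted to Weeks 12, 24, 36 and 52, which all groups share.

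For drug level:

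5. Reconcile Table 2 footnote 6 with Protocol 6.4.16 and 6.6.
6. Where PK and antibody samples already coincide (Weeks 0, 24 and 52 at select sites), show concentration beside the antibody result, negatives included.
7. Add a caution that on-drug negatives (controls through Week 24, and possibly all groups at Day 0) may be masked if drug tolerance is exceeded, and have the sponsor state that tolerance.

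**Cost.** Items 1 to 4 need SAP wording and a few table rows, with no new data. Item 5 is a wording correction. Item 6 uses existing results and may be sparse. Assaying all earlier negative samples is not asked for: retention of immunogenicity serum is not documented, and the 15-year storage text in Protocol Appendix 6 concerns pharmacogenetic samples.

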- 12. Pharmacokinetic sampling at select sites for subjects in the control and treatment holiday groups; subjects in the treatment holiday group can have PK sampling performed at any time during the visit between Weeks 0 and 16. Otherwise, if on a dosing day, sampling must be performed **prior** to dosing. Collect blood samples pre-dose and post-dose at the end of the infusion at Weeks 24 and 52 (or earlier if belimumab is re-started before Week 24 in the event of a severe flare by using the escape option). Subjects in the long-term discontinuation group will have one PK sampling performed at any time during the visit between Weeks 0 and 24. PK sampling for the long-term discontinuation group is not performed after Week 24. Long-term discontinuation subjects withdrawing before Week 24 will have one PK sampling performed at any time during the EXIT visit. PK sampling for long-term discontinuation subjects withdrawing after Week 24 is not performed at the EXIT visit.
- 13. Blood sample for immunogenicity will be taken at Weeks 12, 24, 36 and 52 for all three groups. In addition, a blood sample for immunogenicity will also be taken 4 weeks prior to the reintroduction of belimumab (at Week 20 since belimumab will be reintroduced at Week 24) in the treatment holiday group. A blood sample for immunogenicity must be taken at least 6 months after the final dose of investigational product for any subjects in the control group or treatment holiday group who had an anti-belimumab antibody response at the 16-week follow-up visit (or at the last immunogenicity assessment if 16-week follow-up is not available). Note that serum samples for immunogenicity must be collected pre-dose at the time of dosing from subjects in the treatment holiday group who experience a severe flare prior to Week 24 and consequently receive open-label belimumab as rescue. Immunogenicity blood sample will not be collected at the 6-month follow up visit for subjects in the long-term discontinuation group as this visit does not apply to this subject group.
- 14. Measured in treatment holiday group at Weeks 16 and pre-dose at Week 24. Measured in long-term discontinuation group at Weeks 16, 24 and 32. Not measured in control group.

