8.1.4. Safety Analysis

AEs will be graded for severity by the investigator using Adverse Event Severity Grading Tables (Appendix 6) or the grades in Section 6.4.8, as appropriate. The frequency of AEs will be tabulated by MedDRA system organ class and preferred term and by treatment groups, according to the treatment group that the subjects were assigned to in the BEL116027 study. Additional analysis may be performed based on event rates adjusting for subject-years on study agent. The number of subjects with AEs and the incidence rate of AEs will be summarised in each 6-month time interval. AEs will also be summarised by MedDRA SOCs and preferred terms for those that are considered to be at least possibly related to study agent and those that are considered to be severe (Grade 3 and Grade 4). Discontinuations due to AEs will be summarised.

The frequency of laboratory abnormalities will be tabulated by treatment group. Laboratory values will be assessed for significant changes from baseline. Laboratory toxicity will be graded using Adverse Event Severity Grading Tables when possible. Shift tables will be used to determine if subjects move from normal to abnormal during the course of the study. Shifts of ≥ 2 grades and Grade 3 or Grade 4 laboratory abnormalities will be summarised.

Immunogenicity (anti-belimumab antibodies) will be summarized at baseline and during treatment and follow-up.

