3.42.	ITT	Laboratory Reference Range Shifts from Baseline by Visit: Liver Function (52-Week Treatment Phase)	Benlysta Standard	
3.43.	ITT	Laboratory Reference Range Shifts from Baseline by Visit: Electrolytes (52-Week Treatment Phase)	Benlysta Standard	
3.44.	ITT	Laboratory Reference Range Shifts from Baseline by Visit: Other Chemistries (52-Week Treatment Phase)	Benlysta Standard	
3.45.	ITT	Laboratory Reference Range Shifts from Baseline by Visit: Urinalysis (52-Week Treatment Phase)	Benlysta Standard	
3.46.	ITT	Laboratory Reference Range Shifts from Baseline by Visit: Immunoglobulins (52-Week Treatment Phase)	Benlysta Standard	
Immun	oglobulins			
3.47.	ITT	Immunoglobulin Levels below the Lower Limit of Normal (LLN) by Visit (52-Week Treatment Phase)	Benlysta Standard	
3.48.	ІТТ	Immunoglobulins below the Lower Limit of Normal (LLN) at each Visit among Subjects with Immunoglobulins >= LLN at Baseline (52-Week Treatment Phase)	Benlysta Standard	
3.49.	ITT	Immunoglobulins above the Lower Limit of Normal (LLN) at each Visit (52-Week Treatment Phase)	Benlysta Standard	
3.50.	ITT	Immunoglobulins above the Lower Limit of Normal (LLN) at each Visit among Subjects with Immunoglobulins <= LLN at Baseline (52-Week Treatment Phase)	Benlysta Standard	
Immun	ogenicity			
3.51.	ITT	Immunogenic Response by Visit (52-Week Treatment Phase)	Benlysta Standard	

Safety:	Safety: Tables					
No. Population Title Programming Notes Priority Denoted by H				Headline Results		
Vital Sig	Vital Signs					
3.52.	ITT	Vital Signs Change from Baseline by Visit (Observed) (52-Week Treatment Phase)	ICH E3			

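### The SAP's only anti-drug antibody table stops at the 52-week phase, so the protocol's end-of-study count is not tabulated for the treatment holiday and control groups

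*SAP*

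**What the plan says.** Protocol 6.1.2 lists as a secondary endpoint: "Number of subjects with confirmed true positive belimumab anti-drug antibodies (ADA) by the end of the study". Protocol 8.1.4 states: "Immunogenicity (anti-belimumab antibodies) will be summarized at baseline and during treatment and follow-up". Protocol 6.4.16 also places the reporting of confirmed positives, titers and neutralizing antibodies at the end of the study.

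Sampling matches those intentions. In Year 1, "Blood sample for immunogenicity will be taken at Weeks 12, 24, 36 and 52 for all three groups", with an extra Week 20 sample in TH. Protocol Table 2 also marks samples at the 16-week and 6-month follow-up visits. Protocol Table 3 marks them at Weeks 24 and 48 of each maintenance year.

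The SAP does not agree with itself. Section 2.2 gives the endpoint as "Response (Negative, Transient Positive, Persistent Positive) by Visit and Across All Visits". Section 8.4.2.1, which governs the analysis, says: "Immunogenic response will be summarized by visit and anytime postbaseline for the 52-week treatment phase". Table 3.51 in SAP 13.11.7, the only ADA table, is labelled for the 52-week treatment phase. SAP 8.5 sends maintenance-phase immunogenicity to a subject profile, and Listing 47 lists immunogenicity results with no phase named in its title. For immunogenicity, SAP Table 2 (changes from the protocol) mentions only the endpoint's category, not a shorter window.

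**The concern.** Immunogenicity is a stated secondary objective of a study about stopping belimumab and starting it again. For a TH subject who restarts at Week 24, only the Week 36 and Week 52 samples fall after re-exposure and inside the tabulated window. A TH subject who restarts earlier escapes to maintenance and, under SAP 13.4.1, has no re-start phase, so every ADA result after re-exposure lies outside Table 3.51.

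As planned, a TH or TC subject whose first confirmed positive comes at the 16-week follow-up or in maintenance appears as negative in the endpoint table. The table then answers a narrower question than the protocol's endpoint, and nothing in the SAP tells the reader so.

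The transient/persistent classification is also exposed, because it turns on which sample is the final assessment and that term is not defined.

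**Working it through.** The documents give no ADA rate, so there is no stated figure to reproduce. The check sets the texts side by side and then sizes one misplaced subject.

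1. **Window.** Protocol 8.1.4 covers baseline, treatment and follow-up, and Protocol 6.1.2 runs to the end of the study. SAP 8.4.2.1 and Table 3.51 cover the 52-week phase only. SAP 2.2 covers all visits. The notes in SAP 13.4.1.1 and 13.4.1.2 acknowledge that immunogenicity may be collected at the 6-month visit, and say that this visit does not define a treatment phase.

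2. **Who can have late samples.** SAP 2.3 gives 12 TH, 29 TC and 39 long-term discontinuation (LTD) subjects enrolled: 12 + 29 + 39 = 80. Protocol Table 2, footnote 3, excludes LTD from both follow-up visits, and SAP 13.4.1 excludes LTD from maintenance. At most 12 + 29 = 41 of 80 (51%) can contribute a late result.

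3. **Scheduled samples after Day 0.** TC has 4 in Year 1 plus up to 2 in follow-up, so up to 2/6 = 33% fall outside the table. TH has 5 plus up to 2, so up to 2/7 = 29%. Maintenance adds two per year.

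4. **Which late samples can reveal a first positive.** The 16-week and maintenance samples carry no condition on earlier ADA status. The 6-month sample does: footnote 13 requires it in TH or TC subjects who had a response at the 16-week visit, or at the last assessment if that visit is unavailable. Protocol 6.4.16 also opens it to subjects with no 16-week sample. It is therefore taken mainly in subjects already positive.

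5. **Effect of one late-only positive.** TH: 1/12 = 8.3 percentage points. TC: 1/29 = 3.4 points.

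6. **Chance that the issue arises at all.** The late-only rate is not given, so it is assumed. With rate p and all 41 subjects sampled late, the chance of at least one is 1 − (1 − p)^41. For p = 1%, 2%, 5% and 10% this is 34%, 56%, 88% and 99%. For each assumed rate these are upper bounds, because not every subject will have a late sample.

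7. **Classification.** SAP 8.4.2.1 calls a single positive transient if it is not at the final assessment and persistent if it is. Take a lone Week 52 positive followed by a negative 16-week sample. With the window closed at Week 52 the subject is persistent; with follow-up included the subject is transient. A category can change with no new positive.

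**The case against.** The strongest reply is that nothing is hidden. Listing 47 covers the ITT population without a phase limit in its title, maintenance results go on subject profiles, and SAP 13.3.2 gives the two follow-up visits their own analysis visit numbers. With 12 and 29 subjects, a reader could count late positives by hand. This stands: a reader might infer that late positives go unreported, and the documents do not support that. What is missing is the count in the endpoint table.

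A reader might also infer that the 6-month visit would uncover new positives. Apart from subjects without a 16-week sample, its entry rule makes that unlikely; its main effect is on the transient/persistent split.

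The endpoint's wording is arguable too. The title of Protocol 5.6 places maintenance after the end of the study, and subject completion is set at Week 52, whereas Protocol 9.5 treats the study as complete only after efforts to obtain the follow-up visits. The inclusion of maintenance is therefore open to interpretation. The inclusion of follow-up is not, because Protocol 8.1.4 says ADA "will be summarized at baseline and during treatment and follow-up".

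Nor do the documents show a settled decision to ignore follow-up in the transient/persistent split. The category definitions carry no phase limit and SAP 2.2 points the other way, so this is an unresolved inconsistency.

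Finally, Week 52 is the horizon common to all three groups, while follow-up and maintenance differ in length and attendance. That is a good reason to keep the 52-week summary as the between-group display. It does not justify leaving the protocol's count out.

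**Conclusion.** The mismatch is real and undeclared. No planned table delivers the protocol's end-of-study ADA count for TH and TC, and SAP 2.2 and 8.4.2.1 disagree. LTD is unaffected.

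The consequence is modest. The study is descriptive, late results remain visible in listings and profiles, and the number of late-only positives is unknown and may be zero. Each one would shift the rate by 8.3 points in TH or 3.4 points in TC, taking the enrolled numbers as denominators.

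The conclusion assumes that Table 3.51 follows its title and SAP 8.4.2.1. Counting maintenance samples also rests on reading the end of the study as later than Week 52; counting follow-up samples rests on Protocol 8.1.4 alone.

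**What to change.** - Keep the 52-week summary in Table 3.51 as the between-group display.
- Add a separate descriptive row for TH and TC, 'confirmed ADA at any time to end of study', using all post-baseline samples (maintenance, 16-week and 6-month follow-up). Show the number of subjects sampled in each period.
- Define 'final assessment' for each window, so that the transient/persistent split can be reproduced.
- Align SAP 8.4.2.1 with SAP 2.2 and Protocol 8.1.4. If the 52-week limit is kept as the only tabulation, record it with a reason in SAP Table 2.
- Reconcile the passages on who attends follow-up, since they set the late denominator. The Protocol Summary refers to premature withdrawals. Table 2, footnote 3, is limited to TC withdrawals and to TH withdrawals from Week 24. Section 6 and Table 3, footnote 11, extend to withdrawal during maintenance. Sections 3.1 and 9.5 read more broadly. Footnote 13 and Section 6.4.16 also differ on who gives the 6-month sample.

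The cost is a few SAP sentences and table rows from samples already scheduled. The downside is that the extended window is of unequal length, so the new row should carry a note that it is not for comparison between groups.
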